8.3 Carotid Ultrasound Image Acquisition and Standardization

8.3.1 Equipment and Supplies

- 1) Mindray DC 7 Digital Diagnostics Ultrasound System
- 2) Linear array L7-3 (frequency range: 3-7 MHz) transducer
- 3) Single-lead ECG – contained within the Mindray DC 7 Digital Diagnostics Ultrasound System
- 4) ECG monitoring electrodes
- 5) GE – V100 Vital Signs Monitor (automated blood pressure device)
- 6) Phantom Test Instrument (RMI 404 GS LE, Small Parts Gray Scale-Attenuation coefficients of 0.7

db/cm/MHz)

- 7) Examination table
- 8) Ultrasound conducting gel
- 9) 45° molded head block
- 10) Personal computer
- 11) Back up USB flash drives and portable hard drives

8.3.2 General Ultrasound Procedure and Variability

The above overview (Section 8.2) and following details of our ultrasound techniques/methodology provide a high degree of standardization for image acquisition and processing, resulting in significant reduction in measurement variability between scans; inter- and intra-sonographer coefficients of variation (CVs) <3% (1-5,7,8). Even in multicenter studies with multiple acquisition sites, the methodology is highly stable and reproducible with low variability, <3% CV (11-13).

8.3.3 Baseline CIMT Acquisition Procedure

Carotid Artery (right)

- 1) Turn on the Mindray DC 7 Digital Diagnostics Ultrasound System
- 2) Select the study preset - NAPS
- 3) Check the screen monitor to make sure that the preset parameter settings are as follows:
 - Transducer frequency - 7.0 MHz
 - Power input - 100 %
 - Dynamic range at mid-range - 55
 - Line density - M
 - FOV - W
 - Focus Number - 1
 - THI - off
 - iBeam - off
 - Smooth - 2
 - iClear - 4
 - Persist - 2
 - Gray Map - 5
 - Depth - 38 mm
 - Zoom mode - normal
 - ECG - on
 - TGC - should be fixed in mid-range position
 -
- 4) Press **NEW PATIENT** key on the control panel to begin the CIMT examination and enter the following information on the screen monitor:

- Participant identification number (PID)
- Date
- Visit #
- Study name (NAPS)
- RT (scan of right carotid artery) or LT (scan of left carotid artery)
- DEG - 45° (head angle)
- PLN (head plain) - (enter NT, MT or CT during ultrasound examination)
- Optimal transducer angle - (OTA, degree - enter 0, 15, 30, 45, 55, -5, -10, etc., during ultrasound examination)
- OP - operator's name

5) Prepare the participant for scanning

- Bring the participant into the ultrasound examination room.
- Explain CIMT procedure to the participant.
- Properly position participant in the supine position on the examination table. Remove necklaces and other objects that may interfere with the procedure. Participant's head and neck are anatomically aligned; place support pillows under participant's head, neck or shoulders if necessary.
- Head is wedged between square pillow block on right and 45° wedge pillow on left. Left ear touches wedge pillow. Blocks rest upon shoulders.
- Connect ECG leads: white - right wrist; black - left wrist; green - right leg.
- Check ECG tracing on the screen monitor; adjust the ECG gain so that tracing is at the bottom of the screen and fully visible.

6) Apply small amount of conducting gel to the field of scanning (right neck). Begin scanning.

7) Begin scanning in the transverse plane on the proximal right side of the neck. Stack the right jugular vein and CCA. In this position, the cross-sections of both vessels appear near the center of image (do not capture the transverse image).

8) Maintaining the transverse stacked image of the jugular vein and CCA, move the transducer towards the head. Move through the carotid bifurcation then back to the bulb-distal CCA area.

[figure not shown]
9) Slowly rotate the transducer 90° degrees around the central image line of the stacked jugular vein and CCA, maintaining the jugular vein stacked above the CCA to a longitudinal image. In this position, the carotid artery image will be in a horizontal orientation. Instruct participant to perform a Valsalva maneuver to fully demonstrate the jugular vein and CCA, if necessary (do not capture this image). Keep transducer pressure light and obtain an image that contains the proximal portion of the carotid bulb as well as the mid- to distal- portion of the CCA. Adjust the overall gain to the lowest setting possible to obtain the optimal image (not during Valsalva). Both the near and far wall CCA IMT should be clearly visible.

10) After the 90° transducer rotation, slight transducer angle adjustment may be necessary to obtain the longitudinal optimal transducer angle (OTA) view of the right CCA. Adjust the TGC's and overall gain to obtain the optimal gain. Gain must be as low as possible (optimal gain) and stable throughout CIMT image acquisition. IMT will be brightest when the transducer angle is perpendicular to the vessel wall.

11) Simultaneously optimize the CCA IMT of the near and far walls. Enter from key board the degree of neck extension using one of the following anatomical landmarks as a perpendicular plane to the examination table:

PLN (head plane) - enter any of NT, MT or CT

- a) "NT" = tip of nose to external acoustic meatus
- b) "MT" = tip of mouth to the external acoustic meatus
- c) "CT" = tip of chin to the external acoustic meatus

OTA, degree - enter any of 0,10,15,20,25,30,35,40,45,-5,-10, etc.

- a) 0 = transducer's longitudinal view plane is parallel to the plane of the examination table
- b) 10 = transducer's longitudinal view plane is 10° above the horizontal of the plane of the examination table
- c) -5 = transducer's longitudinal view plane is 5° below the horizontal of the plane of the examination table

12) Repeat steps 7-10 five times to ensure that the OTA image is a high quality CIMT image and repeatable during the scan. Capture at least 5 video clips of the OTA view.

13) Annotate "ANT" on screen monitor. While maintaining the optimized longitudinal image of the CCA, move the transducer away from the OTA in the anterior direction to acquire CCA IMT images and capture 1-2 video clips of the anterior view.

14) Annotate "POST" on screen monitor. Move the transducer away from the OTA in the posterior direction to acquire CCA IMT images and capture 1-2 video clips of the posterior view.

15) Annotate "BIF" on screen monitor. Scan the longitudinal plane view of the bifurcation (carotid artery bulb). Sweep to the anterior direction and then sweep back to the posterior direction. Bring the far wall IMT of the bifurcation into view. Emphasis is placed on optimizing visualization of the IMT and acquiring the thickest IMT image on the bifurcation view. A bifurcation view is defined as an image that contains 100% of the carotid bulb as well as the proximal internal or external carotid arteries. Capture 1-2 video clips of the bifurcation view. Identify the internal and external carotid arteries by Doppler, if necessary. Annotate images to identify structures.

16) Survey the carotid artery for plaques. In the cross section view, move the transducer cephalad (towards the head) from the distal CCA through the bifurcation to the proximal internal and

external carotid arteries then return to the distal DCC. Slowly rotate the transducer 90° to acquire a longitudinal plane view of the carotid artery. Sweep in the anterior direction then sweep in the posterior direction to acquire plaque(s) images, if any. If only one plaque is identified, obtain the maximal carotid plaque thickness (MCPT) and capture 2 video clips. If multiple plaques are identified, label each plaque (as p1,p2,p3...) and obtain the MCPT of each plaque and capture 1 video clip of each plaque. Determine quantitative Doppler at site of all lesions.

- 17) Annotate “Left” on screen monitor. Scan the left side CCA IMT by turning the participant’s head to the right and following steps 6-16.
- 18) Standard output file format: Both AVI and DICOM video clips. Provide at least 16 clips if possible for each scan. This includes:
 - 5 clips - Longitudinal OTA views of the RCCA
 - 1 clip - Longitudinal anterior view of the RCCA
 - 1 clip - Longitudinal posterior view of the RCCA
 - 2 clips - Longitudinal views of the RBIF (IMT)
 - 2 clips - Longitudinal views of the MCPT, if any
 - 3 clips - Longitudinal OTA views of the LCCA
 - 1 clip - Longitudinal anterior view of the LCCA
 - 1 clip - Longitudinal posterior view of the LCCA
 - 2 clips - Longitudinal views of the RBIF (IMT)
 - 2 clips - Longitudinal views of the MCPT, if any
- 19) Prepare the GE-V100 automated blood pressure device. Measure the participant’s upper right arm circumference to select the appropriate blood pressure cuff size. Snugly place the blood pressure cuff on the participant’s right upper arm. Note the mark on the inside of the blood pressure cuff that needs to be placed over the brachial artery. Blood pressure cuff should fit snugly but not so tightly as to prevent venous return between determinations. Press POWER ON and then press INFLATE to begin the automated blood pressure determinations every one minute. Record five sequential blood pressure and pulse rate measurements on the participant’s data sheet.
- 20) Completely and accurately complete the CIMT work sheet.
- 21) Place a back-up USB flash drive or portable hard-drive to the ultrasound system’s tray. Click the [iStation] key on the control panel or click the [iStation] button in the review screen and select the source of the scan database, Find the participant’s PID and scan date in the review screen and select the examination that has been performed. Click [Send To] or [Back-up Patient Record] in the dialogue box and click [OK] or the [Back-Up] button in the dialogue box to begin writing to the system-supported media (Back-up USB flash drive or portable hard-drive). After the writing process is completed, click the symbol in the lower right corner of the monitor screen to eject the back-up USB flash drive or portable hard-drive.

8.3.4 Repeat (Follow-up) CIMT Acquisition Procedure

Use the same ultrasound equipment and transducer during entire CIMT project. Use participant’s baseline CCA, vascular diameter images, carotid artery bifurcation as well as MCPT images, if any as the reference for ultrasound equipment setup parameters and guidance for repeat image acquisition. Repeat image acquisition parameters must be the same as those used for baseline image acquisition including transducer frequency range (MHz), depth, dynamic range, TGC, gain, power, etc., all of which

are automatically recorded on the baseline ultrasound images. The key to image reproducibility is to match the follow-up image to the baseline image as precisely as possible.

Follow the same CIMT acquisition procedure as used for baseline acquisition (See Section 8.3.3, Baseline CIMT Acquisition Procedure) and ensure that the follow up image landmarks look the same as those on the baseline image when performing follow-up image acquisition:

- Top tissue pattern
- Jugular vein pattern
- Bottom tissue pattern
- CCA near-wall IMT pattern
- CCA far-wall IMT pattern
- MCPT pattern, if any

8.4 Automated Computerized Image Analysis of IMT

A computer system developed to assess carotid arterial dimensions from ultrasound images includes a personal computer. Software developed to measure changes in arterial dimensions includes a technique for automated edge detection of the lumen-intima and media-adventitia echo lines for IMT measurements (1-5,7,8). Automated boundary detection provides IMT and luminal measurements with greater precision than manual boundary identification because multiple measurements along the vessel structures replace a single point measurement made with a cursor (7,8). When automated detected edges are observed they do not differ from those chosen by manual analysis although manual variability is considerably greater than that obtained from computer-detected gradient-based edges. A description of the critical parts of the image processing system is given below.

Analysis of each B-mode carotid ultrasound frame involves the steps outlined below.

- 1) Select the frame to be analyzed from the digital frame loop
- 2) Enter the frame identification information (participant ID, date, etc.)
- 3) Manually point to the approximate location of the lumen-intima and media-adventitia echoes for IMT measurements (or the adventitia-media and media-adventitia echoes for arterial diameter measurements) with a mouse
- 4) Automatically track the lumen-intima and media-adventitia echoes and compute IMT (or automatically track the adventitia-media and media-adventitia echoes and compute arterial diameter)

These steps are further discussed below.

Frame selection: Ultrasound image input to the current ultrasound image processing and analysis workstation system is directly through the digital frame loops generated by the digital ultrasound imager. Digital frame loops are played back through the ultrasound image processing and analysis workstation system and optimum frames are selected through direct visualization of individual digitized frames within the digitized frame loop.

Participant and measurement database: The program database has been structured to allow subjective descriptions of image quality and lesion morphology to be stored along with measurements and other process descriptors. The information stored is shown below. Data relating to image quality reflects on the relative reliability of each measurement and is taken into account when the measurements are analyzed. Participant and image information:

Reader (computer operator)	
Participant identification code	
Visit number	
Examination date	
Frame time code	
Side	(left,right)
Segment code	(CC1, CC2, CC3, BUL, ICA, PA, BA)
Measurement code	(near wall, far wall, lumen diameter)
Tracking method	(automatic, manual)
Image quality	
Lumen-intima lesion?	(yes,no)
Wall characteristics, border	
Wall characteristics, density	
Wall characteristics, structure	
Double line visible?	(yes,no)
Measurement made?	(yes,no)

Ultrasound equipment parameter preset values for the ultrasound examination, such as transducer frequency range (MHz), depth, dynamic range, TGC, gain, power, etc. are automatically recorded on the ultrasound video clips, and are recorded separately to establish identical technical conditions for follow-up examinations. This process standardizes instrument setup that encompasses the full dynamic range of the ultrasound echo across all studies within the same participant.

Automated boundary detection: Automatic detection of the lumen-intima and media-adventitia echo lines is difficult because the intensity of the boundary is highly variable and frequently discontinuous. Our software surmounts these difficulties in a three step edge detection process. Additionally, our computer tracking software searches for edges normal to the curvature of the artery.

The first step is to identify the approximate location of the boundary at four to six points using a mouse. A smooth curve fit to these points serves as a guide to the automated edge tracking algorithm.

In the second step of the edge tracking process, the computer examines image intensity values in the image along a series of paths perpendicular to the smooth curve. For each path, the point in the image where the intensity gradient is largest is conditionally labeled as the boundary of the echo along that path. For each boundary point, both the image coordinates and the gradient value are stored.

The third step in the process compares the gradient value for each conditional edge to the maximum gradient value of all conditional edges of the boundary and eliminates those edges with gradient values less than a preselected fraction of the maximum value. This procedure eliminates weak edges and gaps from the boundary.

IMT and lumen diameter measurement: The boundary tracking described above is applied to the lumen-intima and media-adventitia echoes. Since the longitudinal carotid images are nearly horizontal in the ultrasound pictures, wall thickness is measured along vertical image lines at each point of the wall where both boundary points exist. From these data, maximum and average wall thickness is computed. Lumen diameter is measured in the same way as the wall thickness with the boundary tracking applied to the near and far wall media-adventitia echoes.

Lesion size measurements: The lumen-intima ultrasound echo from raised carotid artery lesions are frequently highly irregular and difficult to track with automated edge finding algorithms. In addition, calcium shadowing can obscure the media-adventitia boundary. To deal with these problems, an option

is available to use manual tracing of lesion boundaries with the mouse. When calcium shadowing completely obscures edges, the opposite common carotid artery is used. If this is also unreadable because of shadowing, and manual tracking is also impossible, the case is discarded. In our experience over tens of thousands of ultrasound examinations, this occurs in <1% of participants. The type of tracking used (automatic or manual) is indicated in the database when such measurements are stored.

From the resulting analyses by computer of the B-mode images, thickness of the far wall intima-media and arterial diameters are stored electronically. Our software automatically creates and stores averages, maxima and minima vessel dimensions.

8.4.1 IMT Measurement Standardization

Good IMT image processing derives from good image acquisition.

All settings must be consistently and accurately shown along with the ultrasound scan images for each participant. This information is entered as part of the database during image processing.

Equipment information:

- a) Transducer frequency range (MHz)
- b) Depth (field of view (FOV))
- c) Dynamic range
- d) TGC
- e) Total gain
- f) Power
- g) Ultrasound instrument

Participant information:

- a) Date of scan
- b) Visit number
- c) Participant ID
- d) Study (NAPS)
- e) Date of image processing
- f) Participant's positioning during ultrasound image acquisition
- g) Participant's side scanned (left, right)

Image processing information:

- a) Segment analyzed
 - CC1 - First cm from the proximal carotid artery bulb
 - CC2 - Second cm from the proximal carotid artery bulb
 - CC3 - Third cm from the proximal carotid artery bulb
 - BUL - Carotid artery bulb
 - ICA - Internal carotid artery
- b) Image processor's initials
- c) Frame number analyzed
- d) Ultrasound image description
 - i) Angle variation of the common carotid artery

- ii) Distance of IMT measurement from the proximal carotid artery bulb
- iii) Image name for storage
- e) Measurement code (near wall, far wall, lumen diameter)
- f) Tracking method (automatic, manual)
- g) Image quality
- h) Lesion notation

Image processing calibration:

- a) This may vary from participant to participant (Depth or FOV) and by ultrasound imager
- b) Use the phantom test images to calibrate the horizontal and vertical pixel sizes

Frame selection for image processing:

- a) Frames selected at QRS wave (R-S interval) and T-wave on each heart cycle (paired image)
- b) Frame selected where IMT is brightest and most continuous
- c) Must use the same referencing landmarks on each follow-up visit
- d) Name and save (at least 15 paired images) images

IMT measurement:

- a) A pre-calibrated computer-generated 1 cm electronic ruler is placed above area of interest
- b) Using a mouse, points are marked directly above the lumen-intima echo along the 1 cm ruler length. This represents the first edge
- c) Using a mouse, points are marked directly below the media-adventitia echo along the 1 cm ruler length. This represents the second edge
- d) Steps a through c are repeated for the next consecutive frame (usually the next heart cycle)
- e) Based on the baseline measurement, the same measurement location is made on each follow-up scan (absolutely required)
- f) The image processed baseline scan is viewed during image processing of all follow-up scans to ensure step e

8.5 Automated Computerized Arterial Diameter Analyses

Procedures outlined in Section 8.4 are followed and applied to measurement of arterial diameter during systole (maximum arterial excursion) and diastole (minimum arterial excursion). Arterial diameter is defined from adventitia-media (near wall) to media-adventitia (far wall). Arterial diameter is measured along the same 1 cm segment identified by the computer-generated electronic ruler used for the measurement of IMT.

8.6 Vascular Stiffness

Measurements of right CCA lumen diameters at systole (D_s) and diastole (D_d) are determined at the same site where CIMT is measured (8,14-16). Standardized brachial artery blood pressure measurements are determined using an automated oscillometric method (GE – V100 Vital Signs Monitor) at the end of each ultrasound examination (average of 5 supine measurements) in order to measure systolic (P_s) and diastolic (P_d) pressures and pulse pressure ($PP = P_s - P_d$) (8,14-16). The CV for $D_s = 1.28-2.33\%$, $D_d = 1.18-2.23\%$, $P_s = 6.17-8.75\%$ and $P_d = 6.96-8.77\%$ (8,15). Two indices of arterial stiffness and arterial compliance are calculated as follows:

$$\text{Arterial distensibility} = [2(D_s - D_d)/D_d]/PP$$

$$\text{Arterial compliance} = (D_s^2 - D_d^2)/PP$$

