1.1 Executive Summary

The potential for nattokinase to “thin” blood and to reduce blood clotting by positive antithrombotic and fibrinolytic effects presents a unique opportunity to safely study such effects on cardiovascular disease (CVD) and cognition. Unfortunately, such studies of antithrombotic and fibrinolytic pathways of prevention have been limited due to lack of safe compounds and the adverse reactions associated with current agents such as Coumadin. Nattokinase, an over-the-counter supplement used for cardiovascular health, is the most active functional constituent of natto, a fermented soy product. Natto has been consumed primarily by the Japanese for over 1000 years, a population with one of the lowest risks for CVD and dementia. CVD and dementia remain the most challenging age-related health risks of the 21st century for Americans necessitating development of further effective preemptive strategies. Whether reducing the propensity for thrombus formation and/or increasing fibrinolytic activity can prevent the progression of atherosclerosis and cognitive decline has not yet been determined.

Using nattokinase under primary prevention conditions, we propose to conduct a randomized, double-blinded, placebo-controlled trial to determine whether decreasing atherothrombotic risk can reduce the progression of atherosclerosis and cognitive decline. We propose to randomize 240 healthy non-demented women and men to nattokinase supplementation or to placebo for three years. The primary trial end points will be measurement of carotid arterial wall thickness and arterial stiffness, early changes of atherosclerosis that can be measured safely by non-invasive imaging techniques. The secondary trial end point will be ascertained through change in cognition measured by a neuropsychological battery. In addition, biochemical blood measurements and in vitro studies will be conducted to compare the effects of nattokinase relative to placebo on blood coagulation and thrombus break-down capabilities, blood flow properties, inflammation and inflammatory activation of endothelial cells that line blood vessels.

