1.3 Study Overview

The Nattokinase Atherothrombotic Prevention Study (NAPS) is a randomized, double-blinded, placebo-controlled, non-invasive vascular imaging trial. A total of 240 healthy non-demented women and men without clinical evidence of CVD or diabetes mellitus will be randomized to either placebo or to active oral nattokinase 2,000 fibrinolytic units daily. Recruitment will occur over 2 years and the treatment period will be for 3 years. Candidates will be prescreened, seen for 1 screening visit to determine eligibility and then randomized at a baseline visit. Participants will then return for a follow-up visit 1 week after randomization and then will be followed monthly for the first 6 months and then every 3 months for the remainder of the trial. Rate of change in distal common carotid artery (CCA) far wall intima-media thickness (CIMT) and arterial stiffness in computer image processed B-mode ultrasonograms will be the co-primary trial end points. Cognitive decline determined with a neuropsychological battery designed to evaluate 7 cognitive domains including: attention, concentration, working memory, executive function; visuospatial/visuoconstructive skills; naming/semantic memory; and verbal and nonverbal episodic memory will be the secondary trial endpoint. Other endpoints will include blood pressure, hemostatic, fibrinolytic and hemorheological factors as well as platelet activity and biomarkers for inflammation, monocyte activation, vascular endothelium injury and activation of vascular endothelium by circulating monocytes.

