9.3 Primary Study End Point Data: Carotid Ultrasound Data

The following ultrasound data will be obtained:

- 1) Primary ultrasound end point measurement will be obtained by:

B-mode ultrasonograms in the posterior view for intima-media thickness (CIMT) measurements of the distal centimeter of the right common carotid artery far wall.

- 2) Co-primary ultrasound end point measures will be obtained by:

B-mode ultrasonograms in the posterior view for average diameter measurements during systole and diastole of the distal centimeter of the right common carotid artery lumen. The luminal dimensions will be used to calculate the following stiffness measurements:

$$a) \text{ Arterial distensibility} = [2(D_s - D_d)/D_d]/PP$$

$$b) \text{ Arterial compliance} = (D_s^2 - D_d^2)/PP$$

where, D_s = average diameter in systole; D_d = average diameter in diastole; PP = pulse pressure = systolic BP – diastolic BP

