9.3.2 Study Data

- 1) For each study ultrasound image, the following measures will be obtained:
 - a) Carotid artery IMT, averaged over the distal centimeter of the right common carotid artery far wall (primary trial end point).
 - b) Carotid artery luminal diameter, averaged over the distal centimeter of the right common carotid artery lumen during systole and diastole. Carotid artery diameters will be used in conjunction with pulse pressure to calculate the two measures of arterial stiffness (co-primary trial end points – arterial distensibility and arterial compliance).

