9.6.3 Comparison of On-trial Changes in Laboratory and Lifestyle Variables

Treatment groups will be compared with respect to on-trial levels and on-trial changes in plasma insulin, lipids/CRP, hemoglobin A1c, coagulation factors, rheology parameters and inflammatory variables. Study groups will also be compared for on-trial levels and on-trial changes of other factors that might confound the analysis of primary end point differences. These will include analysis of dietary factors (e.g., total calories, and total calorie-adjusted calories from total, saturated, polyunsaturated, and monounsaturated fats, calories from protein, calories from carbohydrates, and dietary genistein, daidzein, and glycitein), physical activity, cardiovascular risk factors (including blood pressure, smoking status), and use of relevant nonstudy medications (including antihypertensive and lipid-lowering medications). For descriptive purposes, on-trial laboratory, dietary, clinical, and physical activity variables will be computed as the average of all on-trial determinations, weighted by the length of time between determinations. On-trial smoking will be compared as percentage of smokers versus percentage abstainers; average on-trial smoking levels (cigarettes per day) will also be computed for smokers as the average of all on-trial determinations as above. For all laboratory and clinical measures, a change variable will be computed at each on-trial measurement time as: on-trial value minus baseline value. Changes in laboratory and clinical variables from baseline will be compared within each treatment arm using generalized estimating equations to account for the repeated measurements over the study period; the model-specified correlation structure of the repeated measures will be determined by examination of the observed correlation structure. The test that the model intercept differs from 0 will comprise the overall test for significant change from baseline; incorporation of covariates for time periods of the study will test for differential change from baseline over the study period. Comparison of on-trial levels and changes in laboratory and clinical variables across treatment groups will also use generalized estimating equations, with an added covariate for randomized treatment group; interaction terms of treatment group-by-study time period will test whether treatment group differences vary over the study period. Compliance with the study product will be compared across treatment groups, also using generalized estimating equations as described. All analyses will be performed for the entire study sample and for the group of participants whose overall study product compliance is $>80\%$. The significance level for all analyses will be set at a two-sided $\alpha=0.05$.

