9.6.5.2 Co-Primary Efficacy Analysis: Carotid Artery Stiffness Analyses

Statistical methods to evaluate the arterial stiffness outcomes will mirror those specified for the CIMT analyses above. A normalizing transformation will be applied to the arterial stiffness measures prior to analysis if required.

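### Both co-primary stiffness indices depend on blood pressure, so a treatment-related pressure fall could be reported as reduced arterial stiffness; a supportive index with an interval-based interpretation rule is needed

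*Combined protocol and SAP*

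**What the plan says.** Section 9.3.2 makes the diameter measurements into "the two measures of arterial stiffness (co-primary trial end points – arterial distensibility and arterial compliance". Section 8.6 introduces them with "Two indices of arterial stiffness and arterial compliance are calculated as follows", and sections 8.6 and 9.3 give the formulas: distensibility = [2(Ds - Dd)/Dd]/PP and compliance = (Ds² - Dd²)/PP, with "PP = pulse pressure = systolic BP – diastolic BP". Section 8.6 takes the pressures from the brachial artery, as the average of five supine readings at the end of each scan.

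Section 1.1 describes the primary end points as "measurement of carotid arterial wall thickness and arterial stiffness, early changes of atherosclerosis". Section 1.3 adds "Other endpoints will include blood pressure, hemostatic, fibrinolytic and hemorheological factors", so blood pressure is an outcome in its own right.

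On analysis, section 9.6.5.2 states "Statistical methods to evaluate the arterial stiffness outcomes will mirror those specified for the CIMT analyses above". The test is therefore the treatment-by-time interaction of section 9.6.5.1. Blood pressure enters the plan in three further places:

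- Section 9.6.3 compares on-trial blood pressure between arms among factors that might confound the primary result, together with "use of relevant nonstudy medications (including antihypertensive and lipid-lowering medications".
- Section 9.6.5.1 screens blood pressure as a potential confounder and adds it if it qualifies.
- Section 9.6.7.1 relates on-trial blood pressure to the rate of change in stiffness in ancillary models.

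Blood pressure is not named among the mediators in section 9.6.7.3.

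**The concern.** An artery whose wall stiffens with rising pressure is more distensible at lower pressure even when the wall has not changed. If the active arm lowers pressure, or uses more antihypertensive medication, both indices move in the direction that favours treatment. The protocol reads stiffness as an early change of atherosclerosis, so such a result could be taken as benefit to the wall.

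The existing provisions do not resolve this. The section 9.6.5.1 screen appears to concern baseline values, is conditional, and is framed on the CIMT relationship. A baseline value cannot remove a pressure change caused by treatment. Putting on-trial pressure into the model would condition on a post-randomization variable, so it is not a clean remedy. The comparison in section 9.6.3 shows whether pressure differs, but no rule says what follows for the stiffness claim.

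**Working it through.** The documents state no expected pressure effect, wall model or expected change in stiffness, so there is no figure of theirs to reproduce.

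**Inputs.** From the documents: the two formulas, the scan schedule (two baseline scans, then every six months to three years; section 9.3.3) and 240 participants. Assumed: 1:1 allocation (120 per arm), starting pressure 130/80 mmHg, falls of 3/2, 5/3 and 8/5 mmHg, and a curved wall D(P) = Dref[1 + ln(P/Pref)/b] with b = 6, 8 or 12. Dref cancels from every percentage change.

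**One case in full** (b = 8, Dref = 7 mm at Pref = 80, fall 3/2).

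- At 130/80: Dd = 7.0000 and Ds = 7[1 + ln(130/80)/8] = 7.4248. Distensibility = 2(0.4248/7.0000)/50 = 0.002428. Compliance = (7.4248² - 7.0000²)/50 = 0.1226.
- At 127/78: Dd = 6.9778 and Ds = 7.4044. Distensibility = 2(0.4265/6.9778)/49 = 0.002495, or +2.8%. Compliance = 0.1252, or +2.2%.
- The index beta = ln(Ps/Pd)/[(Ds - Dd)/Dd] goes from 8.000 to 7.975, or -0.3%.

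**All cases, curved wall unchanged** (Pref 80 or 100):

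| Fall (mmHg) | Distensibility | Compliance | Beta |
|---|---|---|---|
| 3/2 | +2.7 to +2.9% | +2.0 to +2.3% | -0.2 to -0.4% |
| 5/3 | +4.3 to +4.6% | +3.3 to +3.6% | -0.3 to -0.7% |
| 8/5 | +7.2 to +7.8% | +5.5 to +6.1% | -0.5 to -1.1% |

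A parallel 3/3 fall leaves pulse pressure unchanged and still raises distensibility by 3.4 to 3.8%, so the effect is not only in the denominator.

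**Linear wall.** For a line through the same two starting diameters, a 3/2 fall moves distensibility by +0.2 to +0.3%, compliance by -0.2 to -0.4% and beta by +2.1 to +2.3%. Over falls up to 8/5, distensibility stays under 1% and compliance between about -0.2 and -1.1%.

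**Does a slope analysis remove a step?** Scan times 0, 0, 0.5, ..., 3 have mean 10.5/8 = 1.3125 and sum of squares about the mean 8.969. A step present from month 6 has slope (10.5 - 6 × 1.3125)/8.969 = 0.293 per year per unit of step, so 3 × 0.293 = 88% of it appears as three-year change. A 2.5% step appears as about 0.73% per year.

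**Chance of a significant result from pressure alone** (two-sided 0.05, per-participant slopes, no true slope variation). The slope SD is CV/√8.969 and the standard error of the arm difference is slope SD × √(2/120). At a per-scan CV of 10% the standard error is 0.0043, z = 0.0073/0.0043 = 1.70, and the chance is 40%.

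| Assumed per-scan CV | 2.5% step | 4.5% step |
|---|---|---|
| 10% | 40% | 86% |
| 15% | 20% | 53% |
| 25% | 10% | 23% |
| 35% | 8% | 14% |

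The measurement CVs in section 8.6 imply a per-scan CV of about 11 to 51%, depending on the assumed correlation (0.5 to 0.95) between systolic and diastolic errors. True slope variation lowers these chances: with a slope SD of 4% per year, the 40% becomes 19%.

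**Which rule for beta?** In the curved-wall model, measured beta = b + ln(Pd/Pref), so a pure pressure fall lowers it slightly, in the favourable direction. Beta also shares Ds and Dd with distensibility, so their errors move together. In simulation (120 per arm, assumed noise), beta agreed in direction in 76 to 100% of falsely significant distensibility results. Requiring beta to be significant as well cut the false wall-stiffness claim from 11-92% to about 3-7%. These figures are rough, and the residual error is larger when the pressure fall is large and the noise small.

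**The case against.** The strongest objection is that the mechanism is not in the formulas alone. It needs a curved wall, which the documents do not give. The curve used here is one under which beta is nearly constant by construction. With a linear wall the co-primary indices hardly move, and beta becomes the more pressure-sensitive index. This stands: no index is pressure-free under every wall model, and the plan should say so.

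A second objection is that the plan does look at blood pressure in sections 9.6.3, 9.6.5.1 and 9.6.7.1, and that a null arm difference in pressure would largely dispose of the worry. That also stands, and is why the pressure difference belongs beside the stiffness result. If pressure does differ, however, these provisions do not say how much of the stiffness effect is wall.

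A reader might infer that the plan expects pressure or antihypertensive use to differ by arm. Section 9.6.3 lists them as factors that might confound and will be compared; it states no expectation.

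**Conclusion.** The point holds as a possibility that the planned analysis cannot resolve. Under a curved wall, a fall of 3/2 to 8/5 mmHg shifts distensibility by about 2.7 to 7.8% and compliance by about 2.0 to 6.1% with no wall change, and the slope test keeps most of a step. A 2.5% step raises the chance of a significant result from 5% to between 8 and 40% at per-scan CVs of 35% down to 10%.

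Two stronger readings are not supported. One is that a small pressure effect would be reported as benefit: it could be, but significance is far from certain at these sizes. The other is that the trial's atherosclerosis conclusion would be a pressure artefact: the argument concerns only the stiffness end points, and CIMT, the other co-primary, is untouched.

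The sizes rest on the assumed wall, starting pressure, pressure falls, allocation and noise. This is an inexpensive improvement to interpretation, not an error in the co-primary definitions.

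**What to change.** Keep distensibility and compliance as defined. In section 9.6.5.2:

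- Prespecify beta = ln(Ps/Pd)/[(Ds - Dd)/Dd], computed at every scan, as a supportive measure in the same mixed model.
- Report its treatment effect with a 95% confidence interval, beside the between-arm differences in scan-time systolic, diastolic and pulse pressure.
- Describe a positive result as reduced wall stiffness only if the beta interval excludes no difference in the favourable direction. Agreement in direction alone is not enough. Otherwise, report a change in distensibility or compliance that may reflect blood pressure.
- State that beta is not pressure-free under every wall model.

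Ps, Pd, Ds and Dd are already collected at each scan. The cost is one derived variable, one extra model and a short interpretation rule. The downside is a more guarded claim if the indices disagree.
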